3 STATISTICAL ANALYSIS POPULATIONS

3.1 INTENT-TO-TREAT (ITT)

The ITT population is defined as all subjects who are randomized; analyses of this population will be based on assigned randomized treatment. This population will include all randomized subjects assigned to the group to which they were randomized irrespective of actual treatment administered. The ITT population will be the primary analysis population.

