7 EFFICACY ANALYSIS

Unless otherwise specified, all analyses will be of randomized subjects by treatment group.

No data imputation will be used, except for the ECBL and Lille analyses. For the primary log-rank analyses of the effect of ELAD on OS, the subject's last available study evaluation through Day 91 after the calendar date at which the last subject was randomized will be used. This OS follow-up will draw from data generated by VTL-308 and VTL-308E follow-up data. Every effort will be made to capture the survival status of each randomized subject through Day 91 after the calendar date at which the last subject was randomized.

For the log-rank analysis of the effect of ELAD on OS, the null hypothesis will be that the true survival curves do not differ and will be tested at the two-sided 0.05 level of significance. The primary efficacy analysis will be carried out on the ITT population, and sensitivity analyses will be performed using the mITT, PP and Safety populations. Kaplan-Meier estimates of survival will be generated for both treatment groups, and estimates will be obtained for median survival, 25th and 75th quartiles. A Cox regression analysis will be performed to obtain an estimate of the hazard ratio and corresponding confidence limits. Exploratory analyses of treatment effect within subgroups will be performed.

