7.1 PRIMARY EFFICACY ANALYSIS

7.1.1 Overall Survival (OS) of Subjects with sAH through at least Study Day 91

OS will be assessed using a log-rank analysis of survival data in the intent-to-treat (ITT) population. Protocol VTL-308E will provide additional survival data up to a maximum of 5 years. Kaplan-Meier estimates of survival will be provided, along with estimates of median survival, 25th and 75th quartiles, by treatment group, while a Cox regression analysis will be used to provide estimates of the hazard ratio and its confidence limits. These analyses will also be carried out on the mITT, Per-Protocol (PP) and Safety populations as sensitivity analyses.

In addition, a similar sensitivity analysis for 91-day overall survival will be carried out using overall survival data through Day 91. Subjects who survived at Day 91 are censored at Day 91. Subjects who were lost to follow-up prior to Day 91 are censored at their last contact Study Day.

Although every effort will be made to determine each subject's survival status through the calendar date for the primary analysis of OS, it is possible that some subjects will be lost to follow-up. In the primary OS analysis, such observations will be censored as of the last date when the subject's survival status was known.

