7.2 SECONDARY EFFICACY ANALYSIS

7.2.1 Proportion of Survivors at Study Days 28 and 91

The effect of ELAD on the proportion of subjects who survived at End of Study Days 28 and 91 will be estimated with 95% confidence intervals for the ITT, mITT, PP and Safety population. Analyses will be presented using the last date known alive, leaving subjects who are not known to be dead, in both the numerator and the denominator. Additional analysis will be done for subjects whose Study Day 28 and/or 91 survival status is unknown at the time of database lock. These subjects will not be included in either the numerator or the denominator of the calculation.

7.2.2 Early Change in Bilirubin Level (ECBL) at Study Day 7

There is a strong correlation between ECBL and response to therapy, as demonstrated by the prior studies evaluating the effects of corticosteroids in AH (Mathurin et al. 2003). Post-hoc analysis of the VTI-208 Safety population suggested that there were more ECBL20 Yes subjects in the ELAD-treated group, and the survival of ECBL20 Yes subjects was significantly higher than the survival in ECBL20 No subjects.

A secondary endpoint for the VTL-308 study will be the proportion of subjects who achieve ECBL20 at Study Day 7 in the ITT population. The 20% or greater threshold for the reduction in ECBL, and the 7-day time point, were chosen as this is consistent with prior literature (Lee et al. 2014, Li et al. 2016, López-Velázquez et al. 2014, Louvet et al. 2007, Mathurin et al. 2003, Morris and Forrest 2005) and in the findings from the VTI-208 study. Differences between treatment groups will be analyzed using a Chi-squared test. The same analysis will also be carried out on the safety population as an exploratory sensitivity analysis.

Definition of Early Change in (total) Bilirubin (tBili) Level (ECBL)

Subjects who died within 7 days (including Day 7) will be excluded from the analysis. ECBL (End point minus start point) will be expressed as a percentage of start point.

- For the start point value, “Within 6 hours prior to ELAD start” tBili value and “Day 2” tBili value will be used for ELAD-treated subjects and Control subjects, respectively;

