7.3.3 Outcome Relative to Selected Screening Factors

In addition, exploratory analyses of outcome relative to selected screening factors will be conducted. The overall survival rates at Study Day 28 and Study Day 91 for the ELAD treatment group and the Control group will be provided for the following subgroups:

- Steroid / pentoxifylline / NAC use at Randomization (Yes/No);
- Steroid / pentoxifylline / NAC use during treatment period (Yes/No);
- Steroid / pentoxifylline / NAC use after treatment (Yes/No).

For the ELAD subjects, treatment period is defined as the period from initiation of ELAD treatment to ELAD treatment stopping. For the Control subjects, treatment period is defined as the period from Study Day 2 to Day 7.

7.3.4 Early Change Bilirubin at Different Levels at Study Day 7

In order to further explore the change in bilirubin as a potential surrogate endpoint for studies of new therapeutic approaches to the treatment of sAH, together with findings from VTI-208 that significant differences were observed for all ECBL values between ECBL 10% and ECBL 40% in the Safety population in the VTI-208 study (VTL data on file), additional exploratory analyses will be carried out. The proportion of subjects will be presented by treatment group and by the following bilirubin categories for the Safety and ITT Populations. Differences between treatment groups at each cutoff will be evaluated using a Chi-squared test.

- 0% reduction from baseline in bilirubin (ECBL0);
- 10% reduction from baseline in bilirubin; (ECBL10);
- 15% reduction from baseline in bilirubin; (ECBL15);
- 25% reduction from baseline in bilirubin. (ECBL25);
- 30% reduction from baseline in bilirubin. (ECBL30);
- ECBL as a continuous variable (use median as cutoff).

Furthermore, exploratory analyses will be carried out and the proportion of survivors at Study Days 28 and 91 will be presented by achieving bilirubin reduction (Yes vs No for ECBL0, ECBL10, ECBL15, ECBL20, ECBL25, ECBL30) for overall, ELAD treatment group and Control group using the ITT Population.

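### SAP 7.2: the ITT ECBL20 endpoint drops deaths through Day 7, and the first Day 28/91 survival analysis counts unknown status as alive; expected effects are small, but both rules should be fixed in advance

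*SAP*

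**What the plan says.** **ECBL20.** SAP 7.2.2 names as a secondary endpoint "the proportion of subjects who achieve ECBL20 at Study Day 7 in the ITT population". SAP 3.1 sets that population: "The ITT population is defined as all subjects who are randomized". The ECBL definition then adds: "Subjects who died within 7 days (including Day 7) will be excluded from the analysis". The only sensitivity analysis named repeats the same analysis in the Safety population, so it carries the same exclusion. The fallback rules for missing values deal with missing bilirubin measurements, not deaths. SAP 7.3.4 uses ECBL at other cut-offs and gives no different rule for deaths.

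**Day 28/91 survival.** SAP 7.2.1 first presents the proportions "leaving subjects who are not known to be dead, in both the numerator and the denominator". It then plans a second version, which removes subjects of unknown status from both counts: "Additional analysis will be done for subjects whose Study Day 28 and/or 91 survival status is unknown at the time of database lock". The general rule in SAP 7 reads: "No data imputation will be used, except for the ECBL and Lille analyses". In the 91-day sensitivity analysis of SAP 7.1.1, "Subjects who were lost to follow-up prior to Day 91 are censored at their last contact Study Day", and the primary analysis also censors unknown status. SAP 1.2.2 and 6.1 specify a chi-squared test for the survival proportions, as does Protocol 7.4.1.

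**The concern.** A randomised subject who dies by Day 7 did not reach the ECBL20 endpoint. Removing that subject conditions the comparison on surviving, which treatment may affect, so randomisation no longer protects it. The arm with more early deaths has the more favourable set left.

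Counting unknown status as alive is a single imputation in fact, if not in name. The same subject is censored in the survival analyses and a survivor in the proportions. The arm that loses more subjects gains survivors. The trial is open-label, and SAP 7.1.4 accepts that post-treatment care and behaviour may differ by assignment, so unequal loss cannot be ruled out.

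At stake are two secondary results. If the handling is settled only once the data are known, it can be chosen for the answer it gives.

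**Working it through.** **Inputs.** 75 per arm (SAP 1.3). The SAP gives no ECBL20 rates and no power for these endpoints. For death rates the documents differ. SAP 1.3 has Control one-year survival of 40% to 48% and hazard ratio 0.4. Protocol 7.1 has 0.004 per day and 0.4, which implies Control one-year survival of exp(-0.004 x 365) = 23%. SAP 1.1 gives the SAP precedence, so its rates lead here and the protocol's are shown beside them. Exponential survival is assumed.

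**Check of the SAP's own figure.** ELAD one-year survival at hazard ratio 0.4 is 0.40^0.4 = 69.3% and 0.48^0.4 = 74.6%, against 69.5% and 74.5% stated. It reproduces to rounding.

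**Hazards.** h = -ln(S)/365. Control: 0.0020 (48%) to 0.0025 (40%) per day. ELAD, times 0.4: 0.0008 to 0.0010.

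**Deaths by Day 7.** 75 x (1 - exp(-7h)). Results are in the table.

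**ECBL20 shift.** Let q be the response rate among Day-7 survivors and d = 1 - exp(-7h). Exclusion estimates q; counting deaths as non-response estimates q(1 - d). The change in the ELAD minus Control difference caused by exclusion is qE x dE - qC x dC. Assumed rates: Control 30-50%, ELAD 30-60%, ELAD at least equal. Largest case at SAP rates (40% survival, both 50%): 0.5 x (0.0070 - 0.0174) = -0.5 points. Smallest (48% survival, 30% v 60%): 0.6 x 0.0056 - 0.3 x 0.0140 = -0.1 points.

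**Imbalance by chance.** The probability of a gap of 3 or more early deaths comes from two independent binomials. Each excess death raises its arm's proportion by 0.4 to 0.6 points (22/74 - 22/75 and 34/74 - 34/75, illustrative responder counts); three raise it by 1.2 to 1.9.

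**Unknown counted as alive, Day 91.** Assume a fraction f = 0.10 of an arm has a loss time uniform over 91 days, taking effect only if the subject is alive, and unrelated to prognosis. With S = exp(-91h) and a = (1 - S)/(91h), the bias is f(a - S). Control at 40%: 0.1 x (0.894 - 0.796) = 1.0 points. ELAD at the same setting: 0.1 x (0.956 - 0.913) = 0.4.

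| | SAP 1.3 rates | Protocol 7.1 hazards |
|---|---|---|
| Expected Day-7 deaths, Control v ELAD | 1.0-1.3 v 0.4-0.5 | 2.1 v 0.8 |
| Exclusion lowers ECBL20 difference by (points) | 0.1-0.5 | 0.2-0.8 |
| Probability of a gap of 3 or more deaths | 0.07-0.10 | 0.22 |
| True Day-91 survival difference (points) | 9.7-11.7 | 17.0 |
| Unknown-as-alive bias, Control (points) | +0.8 to +1.0 | +1.4 |
| Unknown-as-alive bias, ELAD (points) | +0.3 to +0.4 | +0.7 |

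With loss in one arm only, the arm difference moves by that arm's bias: up if ELAD loses subjects, down if Control does. Halving f halves the bias.

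**Other rules under the same loss model.** Dropping unknowns gives (1 - f)S/(1 - fa) - S. This is slightly negative, because deaths before loss stay in while survivors lost later leave: -0.8 to -0.9 in Control and -0.4 in ELAD at SAP rates. Kaplan-Meier has no bias if loss is uninformative. If the hazard tripled after loss (an arbitrary stress test, at protocol hazards), the Control bias would be +3.4 for unknown-as-alive, +2.0 for Kaplan-Meier and +0.8 for drop-unknown. No single rule is safe in all cases.

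**Survival by ECBL status.** SAP 7.3.4 also plans that "the proportion of survivors at Study Days 28 and 91 will be presented by achieving bilirubin reduction". Coding early deaths as non-response there would lower survival in the non-response group by construction, by s - sN/(N + d). Here d is total Day-7 deaths, N = (150 - d)(1 - q) and s is the mean of exp(-84h) over arms. For q of 30-50% this is 1.2 to 2.1 points at SAP rates and 2.2 to 3.0 at protocol hazards, even if ECBL is unrelated to survival.

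**The case against.** Bilirubin change is undefined after death, so excluding deaths is a choice of estimand. It is stated in advance, matches the exploratory Lille rule (SAP 7.3.5), and deaths count fully in overall survival. That defends the exclusion as a sensitivity analysis. It does not make the analysed set the ITT set that SAP 7.2.2 names.

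The sizes are modest, and this stands. The 0-10% in SAP 1.3 is a missing-data range for sample size, not a rate of unknown vital status at Day 91. Home visits, back-up contacts, continued contact after withdrawal and record searches (Protocol 5.5.7, 5.5.8, 13.2, 13.4) should keep unknowns few, so 10% is an upper-end assumption. Timing is assumed too: if all the loss fell on Day 1, the bias would be f(1 - S), or 1.7 to 2.0 points in Control and 0.7 to 0.9 in ELAD at SAP rates.

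The no-imputation sentence is also loosely drafted: SAP 7.1.4 imputes steroid dates and SAP 7.3.6 uses last observation carried forward. That is a reason to tidy it, not to leave the conflict.

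Three stronger readings are tempting. A reader might infer that excluding deaths favours ELAD. At either set of planning rates it slightly understates an ELAD advantage, and would flatter ELAD only with more early ELAD deaths. A hypothetical 1 v 6 death split with 25 v 36 responders moves p from 0.026 to 0.068, but an ELAD excess of 5 or more has probability 0.0002 at the protocol hazards. A reader might also infer that unknown-as-alive is the declared main analysis, or the only one. The SAP labels neither version as main and plans the drop-unknown and 91-day censored analyses. Nor do the documents support any effect on the primary analysis.

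**Conclusion.** The point holds at moderate weight. Two secondary analyses handle post-randomisation deaths or unknown status in a way that departs from the SAP's own ITT definition and no-imputation rule. No analysis counts Day-7 deaths as non-response, and none treats unknown status as dead.

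The expected shift is at most about half a point in the ECBL20 difference and about one point in an arm's Day-91 survival at SAP rates; protocol hazards give somewhat more. These figures rest on exponential survival, assumed ECBL20 rates and an upper-end, uniform, uninformative 10% loss. The effects become material only if early deaths or losses differ by arm, and the direction is not fixed.

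**What to change.** 1. In the ITT between-arm ECBL20 comparison only, count death through Day 7 as non-response and keep the exclusion as a sensitivity analysis. Leave the SAP 7.3.4 survival-by-ECBL tables death-excluded. No change is needed for Lille.
2. Keep the specified chi-squared test at Days 28 and 91, and state that it uses subjects with known status. Because that rule has its own small bias, present beside it the Kaplan-Meier Day 28 and 91 estimates and their difference with 95% confidence intervals, extending the SAP 7.1.1 91-day analysis. Report unknown-as-alive and unknown-as-dead as sensitivity bounds, not estimates, and give the number unknown per arm at each day. SAP 4.1 already tabulates Day-91 status; add Day 28.
3. Reconcile SAP 7.2.1 with SAP 7 by naming any retained unknown-as-alive analysis as an exception to the no-imputation rule.

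Cost: SAP wording, a few extra tables and two versions of the ECBL20 variable to keep apart. All data are already collected. Sample size, conduct and the primary analysis do not change.

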7.3 EXPLORATORY EFFICACY ANALYSIS

Exploratory efficacy analyses may include, but not be limited to, analyses of efficacy outcomes based on any subgroups, such as those defined by medical history, and baseline demographics and other baseline characteristics, along with region (USA vs. Europe).

Additional exploratory analyses that may lead to a better understanding of what other factors may or may not influence efficacy outcomes will be conducted. These analyses will be performed on the ITT population and are summarized below. Pending the results of these analyses, further analyses may be conducted.

7.3.1 Transplant-Free Survival

Typically, orthotopic liver transplantation would not take place in patients diagnosed with sAH until the patient has demonstrated at least 6 months of abstinence. However, recent data ([Burra et al. 2010](#)) has suggested that outcomes from liver transplant in sAH patients are at least as good, and in some analyses better, than outcomes for subjects with viral hepatitis or other conditions associated with liver transplantation. In order to accommodate any potential imbalance between transplant rates in the ELAD-treated and Control subjects in the VTL-308 study, transplant-free survival (TFS) will be assessed as an exploratory efficacy analysis.

TFS will be assessed using a log-rank analysis of survival as with the primary efficacy endpoint, using the ITT population. However, unlike the primary efficacy analysis, subjects receiving a transplant will be treated as follows:

- Censored in the analysis at the time of transplant and be dealt with as though they had dropped out of the study following transplant;
- Included in the analysis as an event at the date/time of the transplant (i.e., transplant-free survival).

In addition an analysis will be carried out of the proportion of transplant-free survivors at Study Day 91 using the ITT population. For this analysis, subjects receiving a transplant will either:

- Not be included in either the denominator or the numerator of the calculation of the proportion of survivors (i.e. they will be dealt with as though they had dropped out of the study prior to Study Day 91);
- Counted in the analysis as an event.

7.3.2 Proportion of Survivors at Study Day 28 and 91

The proportion of survivors at Study Day 28 and at Study Day 91 for ELAD-treated subjects will be provided for the following subgroups:

- ELAD treatment duration based on PERF data, defined as total hours during which the ultrafiltrate pump is on (<72 hours vs. ≥72 hours);
- Total amount of ultrafiltrate delivered (dichotomized based on median value);
- Total amount of oxygen utilization by the cell cartridges (dichotomized based on median value);

- Total number of ELAD components exchanged and total number of exchanges for specific components (e.g. UFGs, bubble traps, etc.) (dichotomized based on median value);
- Total blood loss estimated for each subject based on component exchange (dichotomized based on median value).

7.3.3 Outcome Relative to Selected Screening Factors

In addition, exploratory analyses of outcome relative to selected screening factors will be conducted. The overall survival rates at Study Day 28 and Study Day 91 for the ELAD treatment group and the Control group will be provided for the following subgroups:

- Steroid / pentoxifylline / NAC use at Randomization (Yes/No);
- Steroid / pentoxifylline / NAC use during treatment period (Yes/No);
- Steroid / pentoxifylline / NAC use after treatment (Yes/No).

For the ELAD subjects, treatment period is defined as the period from initiation of ELAD treatment to ELAD treatment stopping. For the Control subjects, treatment period is defined as the period from Study Day 2 to Day 7.

7.3.4 Early Change Bilirubin at Different Levels at Study Day 7

In order to further explore the change in bilirubin as a potential surrogate endpoint for studies of new therapeutic approaches to the treatment of sAH, together with findings from VTI-208 that significant differences were observed for all ECBL values between ECBL 10% and ECBL 40% in the Safety population in the VTI-208 study (VTL data on file), additional exploratory analyses will be carried out. The proportion of subjects will be presented by treatment group and by the following bilirubin categories for the Safety and ITT Populations. Differences between treatment groups at each cutoff will be evaluated using a Chi-squared test.

- 0% reduction from baseline in bilirubin (ECBL0);
- 10% reduction from baseline in bilirubin; (ECBL10);
- 15% reduction from baseline in bilirubin; (ECBL15);
- 25% reduction from baseline in bilirubin. (ECBL25);
- 30% reduction from baseline in bilirubin. (ECBL30);
- ECBL as a continuous variable (use median as cutoff).

Furthermore, exploratory analyses will be carried out and the proportion of survivors at Study Days 28 and 91 will be presented by achieving bilirubin reduction (Yes vs No for ECBL0, ECBL10, ECBL15, ECBL20, ECBL25, ECBL30) for overall, ELAD treatment group and Control group using the ITT Population.

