For all subjects randomized, the following key safety factors must be evaluated within 6 hours prior to ELAD treatment initiation, or at End of Study Day 2 (\pm 6 hours) for Control subjects. These include:

- Platelet count;
- International normalized ratio (INR);
- Serum creatinine;
- Evidence of infection unresponsive to antibiotics;
- Hemodynamic instability assessment (blood pressure and MAP);
- Bleeding status;
- Status with respect to ventilation, intubation, or need for hemodialysis.

These factors will be assessed in accord with the pertinent exclusion criteria (2, 3, 4, 7, 9, 10, 15, and 16, relative to the safety evaluation time point) in the VTL-308 Study Protocol (Amendment

1, dated 20 November 2015). Subjects must be assessed within 6 hours prior to ELAD treatment initiation, or at End of Study Day 2 (± 6 hours) for Control subjects, and subjects must continue to be eligible based on these exclusion criteria, at this time point, to remain in the modified intent-to-treat (mITT) population.

In addition, vital signs will be taken, total bilirubin measured and a MELD score will be calculated at this time point.

The standard of care labs may fulfill this requirement provided they are drawn within 6 hours prior to ELAD treatment initiation.

- If an ELAD subject fails to meet these criteria, ELAD treatment will not be initiated, the subject will continue to receive standard of care, and the subject will be excluded from the mITT population;
- If a Control subject fails to meet these criteria, the subject will continue to receive standard of care, and the subject will be excluded from the mITT population.

Subjects randomized to the ELAD group will be treated with ELAD for a minimum of 3 days (72 hours).

ELAD treatment may be interrupted for a period of *less* than 6 hours then restarted with the same set of cartridges provided that, in the opinion of the investigator, the subject remains eligible for treatment. ELAD treatment may be interrupted for a period of *more* than 6 hours but *less* than 72 hours, for example, to allow for the conduct of a diagnostic or therapeutic procedure or for management of an adverse event, or should there be a need to interrupt the use of anticoagulants. Should this circumstance arise, a new set of ELAD cartridges must be used if treatment of the subject will continue, and the subject must meet the same safety eligibility criteria as are required prior to the initiation of treatment.

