8.3 ADVERSE EVENTS

The number and percent of subjects with treatment-emergent adverse events (TEAEs), TEAEs leading to ELAD discontinuation, TEAEs leading to ELAD treatment interruptions, TEAEs classified by their highest relationship to study drug, and TEAEs classified by their maximum severity, will be summarized by treatment group and by MedDRA System Organ Class and Preferred Term. Individual listings of all TESAEs, all deaths, and all TEAEs leading to ELAD discontinuation/interruption will be prepared.

Treatment-emergent adverse events are defined as those AEs with an onset date/time on or after the randomization date/time. The rationale for this is that subjects in both treatment groups are receiving standard of care at the time of Randomization. In addition summary tables of TEAEs and TESAEs will be presented based on treatment and post-treatment study periods. The study periods used in analysis for ELAD-treated subjects will be defined as Pre-ELAD (Randomization date/time to ELAD start date/time), ELAD Treatment (ELAD start date/time to Study Day 7), D8-D14 (Study Day 8 to Study Day 14) and D15-D91 (Study Day 15 to Study Day 91); and for Control subjects, Rand-D2 (Randomization date/time to Study Day 2), D3-D7 (Study Day 3 to Study Day 7), D8-D14 (Study Day 8 to Study Day 14) and D15-D91 (Study Day 15 to Study Day 91). Additional summaries of TEAEs that started between Randomization and ELAD treatment start, and TEAEs/TESAEs that started after ELAD treatment start will be presented by MedDRA System Organ Class and Preferred Term for subjects in the ELAD treatment group. For comparison purposes within these summary tables, TEAEs that started between Randomization and Study Day 2, and TEAEs/TESAEs that started after Study Day 2 will be presented for subjects in the Control treatment group.

Treatment-emergent adverse events will be coded using Medical Dictionary for Regulatory Activities (MedDRA) (Version 18.1) and incidences will be compared between treatment groups using MedDRA Preferred Terms within System Organ Classes. Subjects will only be counted once within each level of summarization.

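### SAP 7.3.3 classes steroid, pentoxifylline and NAC use by treatment windows that differ between arms and do not exist for ELAD subjects never started, so its Yes/No subgroups are not comparable across arms

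*SAP*

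**What the plan says.** SAP 7.3.3 reports survival rates at Study Days 28 and 91, by arm, within three pairs of Yes/No subgroups. The first, use at Randomization, is defined alike in both arms. The other two depend on a treatment period: "Steroid / pentoxifylline / NAC use during treatment period (Yes/No") and "Steroid / pentoxifylline / NAC use after treatment (Yes/No").

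The period is then defined separately for each arm:

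- ELAD: "For the ELAD subjects, treatment period is defined as the period from initiation of ELAD treatment to ELAD treatment stopping".
- Control: "For the Control subjects, treatment period is defined as the period from Study Day 2 to Day 7".

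The parent section, SAP 7.3, sets the population: "These analyses will be performed on the ITT population and are summarized below". SAP 3.1 says of ITT: "This population will include all randomized subjects assigned to the group to which they were randomized irrespective of actual treatment". SAP 2 provides for ELAD-randomized subjects who are never connected: "If an ELAD subject fails to meet these criteria, ELAD treatment will not be initiated". SAP 7.3.3 has no rule for these subjects.

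SAP 8.3 uses different periods: "ELAD Treatment (ELAD start date/time to Study Day 7") for ELAD-treated subjects, and Study Day 3 to Study Day 7 for Control. SAP 8.4 applies the 8.3 periods to concomitant medications and names the same three drugs as being of particular interest.

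**The concern.** A by-arm survival comparison within a drug-use subgroup is readable only if Yes and No mean the same thing in both arms. Here they do not, for three reasons.

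- The Control window is the same for everyone. The ELAD window ends when the run ends, and SAP 2 lists clinical reasons for an early end, such as a bilirubin rise, an adverse event or an indication for hemodialysis. Window length is therefore tied to prognosis in one arm only.
- A Control subject who fails the End of Study Day 2 check still has a window. An ELAD subject who fails the matching check has none.
- Where the window ends moves drug days between the during and after tables.

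At stake is the reading of background therapy in an open-label trial. Protocol 7.3.1 commits the SAP to evaluating standard-of-care differences between groups that may affect outcome. Tables with arm-specific definitions cannot serve that purpose.

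**Working it through.** SAP 7.3.3 gives no figure to reproduce. The check compares the definitions on one clock.

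**Inputs**

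- Study days after Day 1 are 24-hour periods counted from End of Study Day 1 (Protocol 5.5.1).
- Planned ELAD run: minimum 72 h, maximum 120 h, shorter if a discontinuation criterion is met (SAP 2; Protocol 5.4.3.1.2).
- An interruption may last up to 72 h, and the period may then be extended within the 120 treatment hours (Protocol 6.6).
- ELAD start may be later than End of Study Day 3 (Protocol Table 3, footnote 20).

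**Step 1: window length.** Control, Days 2 to 7 inclusive: 6 × 24 = 144 h. Control, End of Study Day 2 to End of Study Day 7: 5 × 24 = 120 h. SAP 7.3.3 does not say which applies.

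| ELAD start to stop | Share of 144 h | Share of 120 h |
|---|---|---|
| 24 h (early stop) | 17% | 20% |
| 72 h | 50% | 60% |
| 96 h | 67% | 80% |
| 120 h | 83% | 100% |
| 192 h (120 h run plus an interruption near 72 h) | 133% | 160% |

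The ELAD window can be shorter than, equal to or longer than the Control window. What is constant is that it varies by subject and the Control window does not.

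**Step 2: the same drug day, classed two ways.** Let ELAD start at End of Study Day 2 and stop at 72 h, which is End of Study Day 5. Use on Study Days 6 and 7 is then after treatment in ELAD and during treatment in Control. A subject whose drug stops on Day 7 with no taper is Yes for use after treatment in ELAD and No in Control. With the same start and a 120 h run, both windows end at End of Study Day 7 and this difference disappears.

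**Step 3: illustration for a drug not yet started.** Assume the same daily start rate r in both arms (the documents give none). The chance of being classed Yes during treatment is 1 − exp(−r × days).

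| r per day | 72 h | 120 h | 144 h |
|---|---|---|---|
| 2% | 5.8% | 9.5% | 11.3% |
| 5% | 13.9% | 22.1% | 25.9% |
| 10% | 25.9% | 39.3% | 45.1% |

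Identical prescribing can thus give different Yes proportions through window length alone. This shows the mechanism; it does not estimate the trial's misclassification.

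**Step 4: subjects never started.** The documents give no rate. An assumed 5% to 15% of the planned 75 ELAD subjects is 3.75 to 11.25, or about 4 to 11. They could be left out of both tables, coded No for use during treatment, or given a substitute window. If they have a worse prognosis than the rest, leaving them out raises ELAD survival in the tables, and coding them No lowers it in the ELAD No row. Nothing in SAP 7.3.3 selects among these.

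**Step 5: the 8.3 and 8.4 periods.** These end at Study Day 7 in both arms, so they avoid Step 2. They are applied in the Safety population, where SAP 3.4 moves ELAD subjects never started to Control, so Step 4 does not arise there. It arises in 7.3.3 because the population is ITT.

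**The case against.** The strongest points on the other side are these.

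- **Steroids are largely covered elsewhere.** SAP 7.1.4 evaluates Day-28 and Day-91 survival by post-randomization steroid use, overall and in four duration bands, with definitions common to both arms. This stands. Pentoxifylline and NAC have no equivalent.
- **Few subjects may change class on steroids.** Protocol 5.4.1.2 calls for 7 days of steroid in both arms unless contraindicated, so most subjects are Yes during treatment whatever the window. If a taper follows, many Controls stopping at Day 7 are also Yes after treatment. This stands as a limit on size.
- **The windows may nearly match.** SAP 7.3.6 and 8 treat End of Study Day 2 as the Control counterpart of ELAD start. On that anchor Control has 120 h, equal to a full uninterrupted run. This removes any general claim that the ELAD window is shorter, but not the dependence on early stopping.
- **The tables are exploratory**, and 7.3.3 specifies no test. This stands.

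A reader might go further and infer that ELAD loses its safety-check failures, so that the tables favour ELAD. The documents do not support that. SAP 7.3.3 states no exclusion, ITT keeps these subjects, and the SAP says so explicitly where it does drop subjects (for example deaths by Day 7 in 7.2.2). Assuming 5% to 15% never started, with 2 to 3 times the hazard of the rest, dropping them would lift ELAD Day-91 survival by 1.0 to 5.0 points at the protocol's Control hazard (69.5% baseline), or 0.7 to 3.8 points at the SAP's one-year Control rates (79.6% to 83.3% baseline). Those are whole-arm shifts under an unstated exclusion and assumed rates, not shifts in any row that 7.3.3 tabulates.

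**Conclusion.** The point holds as a defect of definition. The during-treatment and after-treatment subgroups in SAP 7.3.3 are built on windows that differ by arm, that depend on clinical course in ELAD only, and that do not exist for ITT subjects never started on ELAD. The SAP also uses other periods for the same drugs in 8.3 and 8.4. The Yes/No rows are therefore not comparable between arms.

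The direction and size of the distortion are unknown. They depend on how never-started subjects are coded and how many subjects change class, and the documents give neither. The Step 3 and Step 4 figures rest on assumed rates.

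The scope is narrow: two sets of exploratory tables, mainly for pentoxifylline and NAC. Primary and secondary results are unaffected. This is an inexpensive improvement, not a threat to the trial's conclusions.

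**What to change.** For the by-arm survival tables in SAP 7.3.3:

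1. Classify use in one window common to both arms, Randomization to End of Study Day 7, for all ITT subjects including ELAD subjects never started.
2. Report Day-28 and Day-91 survival among subjects alive at End of Study Day 7 in both arms.
3. Replace use after treatment with status at that landmark, for example on the drug on Study Day 8 (Yes/No). Any use over Days 8 to 28 should not be used: early deaths have less time to be exposed, which builds immortal-time bias into Day-28 survival.
4. State how these windows relate to the periods in 8.3 and 8.4.
5. Keep drug use during the ELAD run, if wanted, as an ELAD-only descriptive summary.

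The cost is SAP wording and minor reprogramming from data already collected. There are downsides: deaths by Day 7 leave these tables, and the fixed window may cut off ELAD runs that start late. Confounding also remains, because drug use after randomization is not protected by randomization under any window. The change removes only the arm-specific part of the problem.
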